K23 Aim 3 MBQR Study Protocol

Brown University School of Public Health

PI: [name]

Study Staff:

[name] (Study Coordinator)
[name] (Teaching and Research Assistant)
[name] (Research Assistant)
[name] (Research Assistant)

Mindfulness Teachers/Interventionists:

[name]
TBA

Funded by: US National Institute of Health K23AT011173, “Developing internet-delivered, mindfulness-based intervention to reduce HIV risk and promote mental and sexual health among young adult MSM”

1. SPECIFIC AIMS (5-year project; Aim 3 highlighted)

This K23 aims to develop an internet-delivered MBI to address minority stress and its negative HIV-related health consequences experienced by young men who have sex with men (YMSM). Specifically, we propose to adapt, refine, and pilot-test an evidence-based MBI, Mindfulness-based Stress Reduction (MBSR), to promote mental and sexual health and HIV testing engagement among distressed, high-risk YMSM. Aims 1-3 will support the subsequent production and evaluation of the adapted intervention. To maximize reach, scalability, and availability to a population that experience challenges seeking in-person counseling and health services, the intervention will also be adapted for internet-based delivery.

Aim 1. Adapt MBSR for distressed, high-risk YMSM using internet delivery, guided by the ADAPT-ITT model. We will conduct iterative phases of formative research including online-based focus groups with YMSM, solicitation of feedback from stakeholders, and revision of intervention protocols. This process will result in the first-draft of an internet-delivered, mindfulness-based intervention protocol for use with YMSM.

Aim 2. Refine intervention protocol by administering adapted materials to distressed, high-risk YMSM ($n=18$) through internet-based open pilot and gather feedback. Following integration of feedback, this process will result in a finalized protocol of an internet-delivered, mindfulness-based intervention protocol for YMSM.

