Aim 3. Examine the feasibility and acceptability of the internet-delivered mindfulness-based intervention (iMBI), called “Mindfulness-based Queer Resilience (MBQR)”, for HIV prevention. We will enroll and randomize a sample of 60 distressed, high-risk YMSM into one of two groups: MBQR intervention ($n=30$) or active control condition ($n=30$). We will aim to over enroll YMSM of color (e.g., Black/Latinx YMSM) and anticipate the group to include **approximately 50-60% Black/Latinx YMSM (or YMSM of color)**. Primary outcomes are **HIV and STI testing** and self-reported sexual risk behaviors. Secondary outcomes are stress biomarker (fingernail cortisol levels), psychological health, minority stress and coping. The study will examine recruitment and retention, number of sessions attended, self-reported at-home practice of mindfulness, completion of assessment, and acceptability of the intervention.

2. Aim 3 Study Design Overview

[figure not shown]
The methodological approach includes a 2-arm trial of MBQR vs. a *health education* control group, with up to $n=30$ per arm (total Aim 3 sample size = up to 60 participants enrolled and randomized). The study is intended to evaluate the impacts of MBQR on the outcomes outlined in the Specific Aims above.

All research assessments will take place digitally using Qualtrics, LLC (Provo, UT, USA) survey management tool. Participants will be sent secure links via email and SMS that can be accessed with their participant identification number. The MBQR intervention classes will be offered online via Zoom by a trained and qualified mindfulness instructor.

Baseline assessment links will be sent to all enrolled participants and completed prior to the start of the interventions. Follow up assessments will be conducted at three time points (post-intervention, 6-months follow up, and at 1-year follow up (for intervention participants only)).

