Participants who were randomized to the control group will be offered a MBQR-hybrid course after the 6-month follow-up assessment is complete. This additional course is optional. Control group members who opt to take MBQR-hybrid will be invited to complete a post-intervention assessment and exit interview. The total length of involvement for control group participants who opt not to take MBQR-hybrid will be around 6-months from the time of enrollment to the time of the final research assessment, while control group participants opting into the MBQR-hybrid will be done with participation in the study around 9-12 months after enrollment. Participants randomized to the MBQR intervention group will be invited to complete a 1-year follow up assessment in addition to the other assessments, thus their involvement in the study will last around 12 months from the time of enrollment. The study interventions last 10 weeks and take place in the first two months of study involvement.

The figure below provides a visual outline of the study flow, including the screening and assessment sequence.

3. Selection Criteria for Aim 3:

The following is the most updated inclusion/exclusion criteria:

- Inclusion criteria:
 - (1) assigned male at birth,
 - (2) being 18 to 34 of age,
 - (3) identify as a cisgender man or nonbinary,
 - (4) reside in the United States,
 - (5) can read and speak English,
 - (6) engaged in condomless anal sex with another man in past 6 months,
 - (7) endorse distress, measured by the PHQ-9 and GAD-7,
 - (8) possess a device (phone, tablet, computer) that allows for online conferencing.
 - (9) HIV-negative at time of screening
- About HIV status: HIV status will be assessed in 2 steps: (1) by self-report in online survey and (2) by rapid HIV testing via Zoom with a trained study RA (optional; other options could include local testing or by self-report). We will provide rapid oral HIV testing in Aim 3. At screening, participants will participate in rapid oral HIV testing (optional), and at post-intervention and follow-up, participants will engage in both HIV and STI testing (see more in HIV/STI testing protocol).
- Exclusion criteria: YMSM will be excluded from the study if they are determined to have symptoms that would prevent them from giving meaningful consent or participate in study activities including any of the following criteria:
 - (1) Significant cognitive impairment
 - (2) Psychosis
 - (3) Imminent suicidal risk

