Baseline Procedures, Enrollment, Run-In, and Randomization

- 1) Baseline Procedures:
 - a. Eligible participants will be asked to complete a baseline survey via Qualtrics that is estimated to take 60-80 minutes to complete (see separate Assessment document for details).
 - b. At baseline they will also be mailed a Cortisol genetic testing kit that will provide them with the necessary equipment to collect a baseline nail sample (see separate cortisol nail sampling protocol for details). Participants will then mail back the completed sample back to the study staff for further processing. Participants will be compensated \$20 for each genetic sample provided.
 - c. Following baseline survey completion, participants are considered as "enrolled and ready to be randomized".
- 2) Run-in Session: Prior to randomization participants will be asked to attend a mandatory 30-minute introduction session via Zoom that will serve as a 'run-in' session for individuals interested in the study. The purpose of this session will be to:
 - a. Provide a brief overview of the randomization process and intervention arms. This includes an emphasis on the time commitment required for the interventions and for the study as a whole.
 - b. Introduce the research team and the course interventionists.

- c. Walk through the HIV/STI self testing and genetic cortisol sampling procedures; remind participants to mail in their samples / submit their results.
- d. Answer any questions.
- e. Allow participants an opportunity to opt out of the study (submitted privately by email, phone, text, etc.) prior to the randomization. Note that participants can withdraw at any time. The run-in session allows participants an additional opportunity to opt out prior to being included in the randomization. This helps with overall group balance and retention.
- f. Participants who complete the baseline assessment and opt in to the study following the run-in session will be included in the randomization; they will be coded as “enrolled and randomized”.

3) Randomization:

- a. Prior to intervention commencement, participants will be randomly assigned to one of two groups: (1) MBQR Intervention group; or (2) a health education control group.
- b. Control group participants who complete the study will be given the opportunity to participate in the intervention (MBQR-hybrid) after the 6-month follow up assessments are completed.

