- c. A covariate adaptive randomization process will be used, balancing groups based on race (white vs. non-white); anxiety/depressive symptomology (high vs. moderate); and gender identity (cis-male vs. non-binary) if sample size allows for this.

4) Care Packages:

- a. Prior to the start of the interventions, all participants (intervention and control) will be sent a study care package, which will contain a yoga mat, condoms, lubricant, raisins, pen, journal, stickers, and a fidget spinner / stress ball, along with a brief description and purpose for each of the items.

Weekly Assessments, Post-Intervention and Follow-up Procedures

1) *Weekly Assessments:* During the 10-week intervention period, participants will be sent invites (via Qualtrics- individualized links) to complete weekly assessments designed to capture: (a) monitoring of sexual risk (condomless sex); (b) monitoring of depression (PHQ-9) and anxiety symptoms (GAD-7); and (c) self-report of weekly/daily practice time spent on intervention. Participants will be compensated \$5 per each weekly assessment completed (up to \$50 total).

2) *Post-Intervention Assessment:*

- a. Similar to the baseline survey, participants will be asked to complete a post-intervention assessment via Qualtrics. The assessment is estimated

to take 60 minutes to complete, and participants will be compensated \$30 for their time.

- b. Cortisol genetic testing kits and STI/HIV self-tests will be mailed out to participants post-intervention. Participants will be compensated \$20 for each completed test (\$40 total).

3) *Exit Interviews (Intervention Group Only):*

- a. Semi-structured interviews with intervention group participants will be conducted one-on-one via Zoom post-intervention to gather qualitative feedback on the study intervention.
- b. Interviews are estimated to take 90-120 minutes.
- c. Participants will be compensated \$40 for their time.

4) *6-month Follow Up Assessment:*

- a. Similar to the baseline and post-intervention surveys, participants will be asked to complete a 6-month follow up assessment via Qualtrics. The assessment is estimated to take 60 minutes to complete, and participants will be compensated \$30 for their time.
- b. Cortisol genetic testing kits and STI/HIV self-tests will be mailed out to participants post-intervention. Participants will be compensated \$20 for each completed test (\$40 total).

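### Does the undefined primary outcome of HIV and STI testing mean that study-supplied, paid tests will be mixed with testing outside the study?

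*Protocol*

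**What the plan says.** Protocol section 1, Aim 3: "Primary outcomes are HIV and STI testing and self-reported sexual risk behaviors". Section 2 adds: "The study is intended to evaluate the impacts of MBQR on the outcomes outlined in the Specific Aims above". The behaviour that the programme is meant to change appears in the opening of section 1: "to promote mental and sexual health and HIV testing engagement among distressed, high-risk YMSM".

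Testing is also part of the study's own procedures:
- **Screening (section 3):** "At screening, participants will participate in rapid oral HIV testing (optional"). Section 4 allows a local clinic test or self-reported status instead.
- **Run-in, before randomisation (section 4):** "Walk through the HIV/STI self testing and genetic cortisol sampling procedures; remind participants to mail in their samples / submit their results".
- **Post-intervention and 6 months (sections 3 and 4):** "at post-intervention and follow-up, participants will engage in both HIV and STI testing (see more in HIV/STI testing protocol"). Self-tests are mailed to both arms. At 1 year they go to the MBQR arm only.
- **Payment (section 6, Compensation):** $20 for testing at each time point. A footnote marked on the T1 HIV-testing line extends payment to tests not done with the study's kit.

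The baseline survey is described as "estimated to take 60-80 minutes to complete (see separate Assessment document for details"), and section 4 calls the post-intervention and 6-month surveys similar to it. The SAP lists feasibility and acceptability measures, to be summarised descriptively, and qualitative analysis of exit interviews. It has no testing variable.

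**The concern.** A primary outcome normally comes with a variable, a data source, a time window and a scoring rule. Here there is only a name. Nothing says whether study-supplied tests count, how far back the question reaches, or whether HIV and STI testing are scored together.

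This looks more serious because the study supplies and pays for the very act it names as its outcome, in both arms and at the time points where the arms could be compared. If kit tests and outside tests were counted together, high kit uptake in both arms would hide a difference in self-initiated testing. Unequal uptake could create a difference where none exists. If the surveys never ask where a test was obtained, its origin cannot be recovered later. A misread testing result would then pass into the later evaluation that this pilot is meant to support.

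**Working it through.** **1. What the documents would produce.** The plan has no testing rate, effect size, power or significance level, so there is no figure to reproduce. The text can be checked directly:

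| Question | What the documents give |
|---|---|
| Which tests are recorded after randomisation? | Study-mailed HIV/STI tests, with payment on completion (Protocol sections 4 and 6) |
| Are outside tests recorded after randomisation? | Not described; clinic testing appears only as a screening alternative |
| Are kit and outside tests pooled? | Not described |
| Where would the detail be? | The HIV/STI testing protocol (sections 3 and 4) and the Assessment document (section 4), neither available here |
| Is a between-arm analysis of testing planned? | No (SAP) |

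Mixing needs two steps, recording outside tests and pooling them with kit tests. Neither is described. On the data described, the measure is study-test completion alone. The documents therefore support *could mix*, not *would mix*.

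The weekly surveys do not settle it. Their listed content, "a) monitoring of sexual risk (condomless sex); (b) monitoring of depression (PHQ-9) and anxiety symptoms (GAD-7") plus practice time, is monitoring during the ten-week course. Its silence on testing says little about the separate 60-minute assessments at post-intervention and 6 months.

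**2. What pooling would do, on assumed rates.** Let p be the proportion testing outside the study and k the proportion using the kit among the rest. The pooled rate is p + (1 − p)k. With the same k in both arms, the pooled difference is (p_MBQR − p_control)(1 − k). Assume p = 0.40 in control and 0.65 in MBQR, with 30 per arm (section 2). The 95% half-width is 1.96 × √[(p₁(1 − p₁) + p₂(1 − p₂))/30].

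- k = 0.5: 0.70 vs 0.825, difference 25 × 0.5 = 12.5 points, ± 21.3.
- k = 0.8: 0.88 vs 0.93, difference 25 × 0.2 = 5 points, ± 14.8.
- k = 0.9: 0.94 vs 0.965, difference 25 × 0.1 = 2.5 points.
- Unequal k (control, MBQR): 0.5 and 0.9 give +26.5; 0.7 and 0.5 give +0.5; 0.9 and 0.5 give −11.5.

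The last case needs kit uptake to be much higher in control, which nothing in the documents suggests.

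**3. Whether counting outside tests alone is safer.** Kits may replace tests that participants would otherwise have sought. If a share d of outside tests is displaced, the outside rate is p(1 − d) and the difference is (p_MBQR − p_control)(1 − d).

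- d = 0.5: 0.20 vs 0.325, 12.5 points, ± 22.0.
- d = 0.8: 0.08 vs 0.13, 5 points, ± 15.5.

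This is the same shrinkage as pooling with k = 0.5 or 0.8, with slightly wider intervals. Outside testing alone is not clearly the better measure.

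**4. Whether the split is clean.** At least at T1, the study pays for HIV tests done without its kit. A study-paid clinic test is neither kit completion nor plainly outside the study. Dividing tests into paid kit and outside leaves it without a category.

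**The case for a change.** The strongest reply is that two different situations can look the same when tests are pooled. Suppose (A) a 25-point effect on outside testing with kit uptake of 50% in both arms: the pooled result is 70% vs 82.5%, or 12.5 ± 21.3 points. Suppose instead (B) no effect on outside testing, 40% in both arms, with kit uptake of 50% vs 70%: the pooled result is 70% vs 82%, or 12 ± 21.4 points. Reported separately and without displacement, A shows 25 ± 24.5 points for outside testing and 0 ± 25.3 for kit completion; B shows 0 ± 24.8 and 20 ± 24.3. Separate reporting shows where a difference arises, and it costs little if the surveys already ask.

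That logic is sound, and the gap in definition is undisputed. Section 2 does say that the study is to evaluate impacts on these outcomes, so a testing result may be reported.

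Three things limit it. The separation depends on survey items that the Assessment document may already contain, so new items cannot be shown to add anything. The clear contrast holds only without displacement; otherwise displaced tests reappear as kit completion. And outside testing would be self-reported by participants who know their arm. The absence of study STI testing at baseline adds nothing, because a randomised comparison of later testing does not need it.

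**Conclusion.** No change to the plan follows. The protocol and SAP leave HIV and STI testing undefined, and a measure built from study tests would show completion of a supplied, paid test rather than testing outside the study. That is a limit on interpretation, and study-test completion is itself a legitimate measure of testing engagement.

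No planned analysis would come out wrong. Aim 3 concerns feasibility and acceptability, the SAP is descriptive, and neither document rests a sample size or a hypothesis test on testing rates. An analyst reporting testing can be expected to say which tests were counted, over what window and from what source, and to keep outside tests apart from study tests if both were recorded.

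The size is unknown from the documents. The shrinkage from 25 points to 12.5, 5 or 2.5 rests on assumed outside-testing rates, equal kit uptake in both arms and pooling that no passage describes. With 30 per arm, the half-widths calculated above run from about 15 to 25 points, so any of these measures would be descriptive only. The conclusion also assumes that the two separate documents hold the survey and testing detail referred to them. If they do not, the gap still affects only how a testing result is read.

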- 2) Zoom Screening Interview #1: Trained research staff will then follow up with eligible participants to schedule a Zoom-based screening interview (the first of two). This interview will take 10-25 minutes to complete and will serve the following purposes: (a) Review the Informed Consent Form and study procedures; (b) Answer any questions the participant might have; (c) Confirm participant eligibility; and (d) Inform the participant (if eligible and interested) of the next steps, including scheduling the second Zoom screening interview. The study RA will then mail out a HIV self-testing kit to the participant along with testing instructions (see HIV/STI testing protocol).
- 3) Zoom Screening Interview #2: This second Zoom interview will take place 1-2 weeks after the initial Zoom call to allow for the HIV test to arrive in the mail. The participant will be encouraged to find a private location for the call where they will have access to a bathroom for HIV self-testing. The call will take 20-30 minutes and will involve having the participant complete a HIV self-test. The study RA will walk the participant through the testing procedures (or provide participant with a prerecorded instruction video).
 - a. Staff performing Zoom calls will be trained in providing HIV-counseling in the event that the test result is HIV-positive.

- b. If HIV-negative, the RA will go over the next study steps with the participant, including inviting the participant to complete baseline survey via Qualtrics.
- c. If excluded, RA will record reason for exclusion.
- d. Alternative HIV testing procedures include:
 - i. Completing a self-test on one's own and sending a picture to our study Qualtrics link (or sharing results on Zoom)
 - ii. Testing at a local HIV clinic
 - iii. Opting out of HIV self-testing and instead self-report status

Informed Consent

Informed consent is an ongoing process. Participants will first be presented with the Informed Consent Form (ICF) at the time of initial online screening. They will have the option to download and save the ICF and will also be prompted to click through the ICF text in full (displayed on multiple screens in Qualtrics). The consent process will continue into the Zoom Interviews #1 and #2, where a trained research staff member will review the ICF with the participant and answer any questions they might have. A waiver of documentation of consent will be requested since data collection procedures all take place online.

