Randomly generated participant identification (PID) numbers will be automatically generated and assigned through Qualtrics at screening. All questionnaires and tasks will be completed under the assigned participant identification numbers. Consent forms and personal identifiable information will be kept separate and securely away from participant identification numbers in a secure digital file on closed network servers (i.e., Brown Stronghold).

Safety Monitoring

Oversight of internal monitoring of the participants' safety will be conducted by the PI, [name], who is a licensed psychologist.

Entities Conducting Monitoring: The Institutional Review Board (IRBs) at Brown University will review all research procedures and will provide oversight. Internal monitoring will be done by the Brown University principal investigator ([name]) and the Brown University IRB. Any serious adverse effects will be immediately reported to the principal investigator ([name]).

What is Monitored: Monitoring is done of all procedures to ensure that they conform to the approved protocol; of unforeseen circumstances that might arise and affect safety; of all reports of serious adverse events as defined in US Department of Health and Human Services regulations for the protection of human research subjects 45 CFR Part 46, and the FDA 312.32 (death, life-threatening experience, new or prolonged hospitalization, persistent or significant disability/incapacity); of other significant adverse events (adverse events that lead to drop out by participant or termination by the investigator); of unexpected adverse events resulting from the study; and of expected adverse events.

Monitoring is done of all study inclusion and exclusion criteria. During this clinical trial, we will notify officials, as mandated by law, if a participant reports intention to harm him/herself or others, or reports child abuse or abuse of an elder.

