Meditation-related risks: The National Center for Complementary and Integrative Health (NCCIH) states that meditation is generally safe for healthy people, but that adverse effects have also been reported.³⁴ Undesirable side effects and risks of meditation have been documented in more than 40 scientific reports [for reviews see³⁵⁻³⁷] and are listed in the Mindfulness-Based Intervention Guidelines.^{38,39} More common, less serious side effects that have been reported by individuals within the context of MBIs or of individuals who are meditating less than an hour per day include: increased depression, anxiety or panic, re-experiencing of traumatic memories, dissociation, executive dysfunction, headaches/body pain and insomnia.^{35,40-45} A few case reports of more serious side effects including mania, psychosis, and suicidality have been reported, mostly in the contexts of intensive retreats (>5 hrs/day) or in conjunction with pre-existing psychopathology.^{35,37,38,46} The frequency of serious adverse effects in the context of MBIs is estimated to be less than 1%, although adequate estimates are not available.⁴⁷

A number of actions have been taken to minimize meditation-related risks at different stages of the study. During the pre-enrollment stage, individuals with severe mental illness that could preclude regular class attendance or impact group participation (i.e., symptomatic, untreated bipolar disorder or a history of psychosis and/or schizophrenia) are excluded from the study and all risks are clearly communicated in the consent form. During treatment, meditations are relatively short and interspersed with dyads and reflections. Mindfulness homework assigned as part of the intervention is optional and is recommended to not exceed 1 hour per day. Teachers query participants about their experiences with meditation, and provide corrective feedback or modifications when needed. Developing strategies for working with physical and emotional discomfort is an explicit goal of the program. Because not all participants feel comfortable disclosing difficulties in class, an online “safety check-in” questionnaire will query meditation-related risks.

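### The protocol's current eligibility list and its risk section name different psychiatric exclusions, notably for past psychosis without present symptoms

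*Protocol*

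**What the plan says.** Protocol section 3 (Selection Criteria for Aim 3) opens with "The following is the most updated inclusion/exclusion criteria". Its exclusion paragraph removes people found to have "symptoms that would prevent them from giving meaningful consent or participate in study activities including any of the following criteria". Three items follow: significant cognitive impairment, psychosis (with no time frame) and imminent suicidal risk.

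Protocol section 6, Meditation-related risks, introduces its safeguards with "A number of actions have been taken to minimize meditation-related risks at different stages of the study". The first of them applies before enrolment to "individuals with severe mental illness that could preclude regular class attendance or impact group participation". A parenthesis opening with *i.e.* then says who these people are: "symptomatic, untreated bipolar disorder or a history of psychosis and/or schizophrenia) are excluded from the study".

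The next paragraph of section 6, Psychological distress, expects low risk partly because screening questions will remove people with substantial mental illness. It does not define that term.

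On how eligibility is applied, section 4 gives staff at Zoom Screening Interview #1 the task "Confirm participant eligibility". Section 6 (Safety Monitoring) adds "Monitoring is done of all study inclusion and exclusion criteria". The SAP does not mention eligibility.

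**The concern.** Both statements are written as rules in force, yet they name different groups. Section 6 excludes on a history of psychosis or schizophrenia and on one form of bipolar disorder. Section 3 turns on symptoms that the person has, and names neither bipolar disorder nor schizophrenia.

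The difference bears on safety because the protocol itself ties the exclusion to harm. The risk text cites case reports of mania, psychosis and suicidality, mostly in intensive retreats of more than 5 hours a day "or in conjunction with pre-existing psychopathology". MBQR includes a 6-hour retreat (section 5). If section 3 governs because it is labelled current, the low-risk argument in section 6 rests in part on an exclusion that the eligibility list does not clearly contain. If section 6 governs, staff who confirm eligibility from section 3 are using an incomplete list. In either case, monitoring of the criteria has no single reference.

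**Working it through.** No arithmetic applies. The check sets the three statements side by side and then runs example applicants through them.

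| | Section 3 list | Section 6, Meditation-related risks | Section 6, Psychological distress |
|---|---|---|---|
| Status | Labelled current | Rule applied before enrolment | Refers to screening questions |
| Functional test | Symptoms *would* prevent consent or participation | Illness *could* prevent attendance, or affect the group | None |
| Psychosis | Named, no time frame, under a lead-in about symptoms | Named, by history | Not named |
| Schizophrenia | Not named | Named, by history | Not named |
| Bipolar disorder | Not named | Named, if symptomatic and untreated | Not named |
| Cognitive impairment, imminent suicidal risk | Named | Not named | Not named |

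Four applicants show where the two rules agree and where they part:

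1. *Present psychosis.* Excluded by both.
2. *Symptomatic, untreated bipolar disorder that would prevent participation.* Excluded by both, although section 3 reaches it only through its open-ended lead-in.
3. *Symptomatic, untreated bipolar disorder that could affect the group but would not prevent consent or participation.* Excluded by section 6. Not reached by section 3, whose test is stricter.
4. *Past psychosis or schizophrenia, no present symptoms, able to consent and take part.* Excluded by section 6, which names history. Not reached by section 3, because the lead-in asks for symptoms that prevent consent or participation and there are none.

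The fourth case is the clearest. Two staff members, each following one section exactly, would decide differently on the same person. The term in the Psychological distress paragraph does not settle it, because that term is undefined.

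The later safeguards do not settle it either. The weekly PHQ-9 and GAD-7 (section 4), the one-on-one calls with the instructor (section 5) and the online safety check-in (section 6) all operate after enrolment.

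**The case against.** The strongest reply is that the texts are incompletely cross-referenced rather than contradictory, and that both can be obeyed by applying both.

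- *Section 3 is not exhaustive.* Its list is introduced with *including*, so symptomatic bipolar disorder can fall under the general wording. This stands for the second applicant above, and it makes bipolar disorder the weaker part of the concern. It does not help with the fourth, who has no symptoms for the lead-in to catch.
- *Psychosis in section 3 has no time frame and might include history; schizophrenia is a psychotic disorder.* The second part stands: the missing word schizophrenia adds little beyond the question of current against past. On the first part, the item sits under a lead-in about symptoms a person has, so present illness is the natural reading. If history is meant, the list needs to say so.
- *Section 6 also has a functional test.* True, but its *i.e.* defines the group meeting that test, and does so by history.
- *Substantial mental illness is only shorthand for the preceding paragraph.* That is plausible, and makes this a secondary point. The paragraph still relies on the exclusion for its risk estimate.
- *The screening form and interview guide may already ask about history and bipolar disorder.* They may. They are not in the documents, so enrolment of an excluded person is a possibility, not a demonstrated event.
- *Section 3 does cover psychosis and imminent suicidal risk.* It does, so the safeguard is partly present. What is missing is the historical element and the explicit mention of bipolar disorder.

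**Conclusion.** The concern holds. The protocol has two stated psychiatric exclusion rules that give different answers for at least one plausible applicant: past psychosis or schizophrenia without present symptoms. This rests on reading the section 3 lead-in as referring to present symptoms and the section 6 parenthesis as a definition; both are the ordinary meaning of the words. The omission of bipolar disorder by name and the undefined third term are secondary.

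The practical size is unknown. The documents do not give the number of applicants affected, and it could be zero. No sample size, error rate or planned analysis depends on the point; the SAP plans only descriptive summaries of feasibility and acceptability and a qualitative analysis of interviews. What is affected is who may enter the trial and whether the stated safety basis is true of the people enrolled. It should be fixed, but it does not threaten the analysis.

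**What to change.** Reconcile section 3 with both paragraphs of section 6 so that the protocol contains one set of psychiatric exclusions. For each condition, say whether it refers to current symptoms or to history, and whether a functional test also applies. The full set could stand once in section 3 and be cited from the risk text, provided that the terms are the same throughout. Then check the online screening form and the interview guide against that set. The sponsor and the IRB decide what the set should be; this review does not propose one.

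The cost is a short protocol amendment. If the wider wording is kept, some additional applicants may be screened out (possibly none). If the narrower wording is kept, the risk statement in section 6 has to be rewritten without the exclusion it now cites, and becomes slightly less favourable.
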